APPENDIX SECTION:

APPENDIX A INFORMED CONSENT

APPENDIX B ELIGIBILITY CHECKLIST

APPENDIX C COMMON TOXICITY CRITERIA

APPENDIX D ECOG PERFORMANCE STATUS

APPENDIX E CASE REPORT FORMS

APPENDIX F TREATMENT GUIDELINES PRE- NIST CHANGES

APPENDIX G TREATMENT GUIDELINES POST-NIST CHANGES

1.0 OBJECTIVES

1.1 PRIMARY OBJECTIVE:

1.1.1 To evaluate if Xofigo can reduce symptomatic skeletal events (SSE) in patients with NSCLC and bone metastases who have had stable or responding disease following initial systemic chemotherapy.

1.2 SECONDARY OBJECTIVES:

1.2.1 To evaluate toxicity of Xofigo in patients with NSCLC and bone metastases following front-line chemotherapy.

1.2.2 To evaluate time to symptomatic skeletal events.

1.2.3 To evaluate changes in health-related quality of life, using the EORTC QLQ-C30 and QOL-BM22 questionnaires, in patients with NSCLC and bone metastases treated with Xofigo.

1.2.4 To evaluate the impact of treatment with Xofigo on alkaline phosphatase levels in patients with NSCLC and bone metastases.

1.2.5 To measure progression-free survival and overall survival of patients with NSCLC and bone metastases and stable or responding disease after front-line chemotherapy treated with Xofigo.

2.0 BACKGROUND

Non-Small Cell Lung Cancer (NSCLC): Lung cancer is the most common cause of cancer death worldwide, with an estimated 1,600,000 new cases and 1,380,000 deaths per year.¹ In the United States, there are an estimated 228,000 new cases of lung cancer and 159,500 deaths, yearly.²

Bone Metastases from NSCLC: Approximately 50% of patients with advanced lung cancer will develop progressive bone metastases during the course of their illness.³ Bone metastases from NSCLC are frequently symptomatic leading to significant morbidity due to pain, pathologic fracture and neural compression. Primary treatment has relied upon radiation therapy.³⁻⁶ Local external-beam radiation can be effective in patients with a small number of metastases, but its clinical utility in patients with disseminated metastatic bone disease is limited by the number of sites that can be treated. The potential for toxicity to neighboring tissues at an effective radiation dose can also limit retreatment to certain sites. Chemotherapy can be helpful until the disease becomes refractory.³

Bisphosphonates and Denosumab in NSCLC and Bone Metastases: Bisphosphonates have a modest impact in reduction of skeletal related events in NSCLC and other solid tumors.⁷⁻⁹ In the phase III study of zoledronic acid for patients with bone metastases from solid tumors, the time to a skeletal related event was increased from 163 days to 230 days with zoledronic acid versus

placebo. In this study, approximately 40% of patients with bone metastases from NSCLC had a new skeletal related event within 4 months.^{7,8}

The monoclonal antibody denosumab also demonstrates a modest benefit in reduction of skeletal events in NSCLC.^{9,10} Denosumab binds to RANKL inhibiting osteoclast formation. Bisphosphonates and denosumab act primarily on osteoclasts and do not treat metastases directly. Furthermore, they each are associated with osteonecrosis of the jaw.⁷⁻¹⁰

Radium-223 (Xofigo): Xofigo is an alpha-particle emitting radiotherapeutic drug (radium-223 dichloride) which mimics calcium and forms complexes with hydroxyapatite at areas of increased bone turnover, such as bone metastases.¹¹ Xofigo targets bone metastases by delivering high-energy, short-range (<100 um) alpha-particles. These alpha particles can potentially provide greater dose to the exact site of bone metastases while also reducing marrow toxicity due to their shorter path length.¹² The phase III, double blind ALSYMPCA study randomized patients 2:1 to receive Xofigo, 6 injections every 4 weeks or placebo. Xofigo significantly improved overall survival in patients with castrate resistant prostate cancer (median overall survival 14.9 versus 11.3 months; P < 0.001).¹¹ Xofigo significantly delayed time to first symptomatic skeletal events including reducing pathologic bone fracture, spinal cord compression, need for surgical intervention for a bone metastasis, and time to external beam radiotherapy. Xofigo also reduced pain and opioid use.

Standard Front-line Treatment of NSCLC and Optimal Role for Xofigo: The initial treatment for patients with metastatic NSCLC who do not have a driver mutation (EGFR or ALK mutation) involves combination chemotherapy for 4-6 cycles with agents such as cisplatin, carboplatin, paclitaxel, pemetrexed.^{13,14} For patients with stable or responding disease, maintenance chemotherapy with pemetrexed or docetaxel may be utilized.¹⁵ After initial front-line chemotherapy, patients with stable or responding disease are often given a treatment break from chemotherapy and followed symptomatically and radiographically. In patients with bone metastases, denosumab or zoledronic acid are commonly administered to reduce symptomatic skeletal events but their effects are on osteoclasts and do not directly treat metastases. Their effectiveness is very limited with approximately half of all patients expected to have new symptomatic skeletal events within the next 4 months.^{7,8} It is within this period following completion of front-line chemotherapy that this protocol will investigate Xofigo.

3.0 PATIENT ELIGIBILITY

3.1 Conditions for Patient Eligibility

3.1.1 Age \geq 18 years.

3.1.2 Advanced non-small cell lung cancer with bone metastases.

3.1.3 Stable or responding disease after completion of initial systemic chemotherapy as defined by RECIST criteria. “Initial systemic treatment,” is to include all treatment and therapy given before a patient progresses. Therefore, a patient may receive different agents, including radiation, as part of their initial treatment as long as they have not and do not progress at any point prior to BrUOG 301 enrollment. However, patient must have received chemotherapy. Site to submit pre-treatment scan with post treatment scan for RECIST and confirmation to BrUOG. Document

blastic or lytic lesions (and for lytic soft tissue or no soft tissue component. Soft tissue component requires measurements for RECIST).

3.1.4 At least 3 weeks must have elapsed since completion of last chemotherapy and 4 weeks since last radiation, prior to first dose of Xofigo. Patients are not permitted to receive any form of 'maintenance' chemotherapy or biologic/targeted anticancer therapy while being treated on this study

3.1.5 Life expectancy of at least 12 weeks (3 months).

3.1.6 Patients with treated brain metastases are allowed, but must have brain imaging showing evidence of stability since most recent treatment for brain mets, prior to first dose of Xofigo. For patients with brain metastases only, brain imaging is required as per section 6 and scan must be sent to BrUOG with registration information before patient is registered on study. Patients who do not have brain metastases or symptoms of potential brain metastases are not required to have baseline brain imaging, but this must be confirmed in writing to BrUOG at time of registration.

3.1.7 Eastern Cooperative Oncology Group (ECOG) Performance Status of 0 – 1.

3.1.8 Required entry laboratory parameters within 14 days of study entry: White Blood Cell Count (WBC) \geq 3,000/mm³; Absolute Neutrophil Count (ANC) \geq 1,500/mm³; Platelet (PLT) count \geq 100,000/mm³; Hemoglobin (Hgb) \geq 9g/dL, Total bilirubin level \leq 1.5 x institutional upper limit of normal (ULN); Aspartate aminotransferase (AST) and alanine aminotransferase (ALT) \leq 2.5 x ULN ; Creatinine \leq 1.5 x ULN; Albumin $>$ 2.5 g/dL.

3.1.9 Concurrent treatment with bisphosphonates and denosumab is allowed. Information on start and stop date and drug with dose to be sent to BrUOG if patient to be treated concurrently.

3.1.10 Prior skeletal related events (pathologic fracture, radiation or surgery to bone, or spinal cord compression) are allowed if they have been managed and now patient is stable for 4 weeks prior to study entry. Must submit how events managed to BrUOG for documentation to confirm eligibility criterion. (For example, if a patient experienced a SSE and had radiation for 2 weeks they must then be stable for 4 weeks after the completion of radiation prior to study entry)

3.1.11 Subjects must be able to understand and be willing to sign the written informed consent form.

3.1.12 All acute toxic effects related to prior treatment(s) must have resolved to NCI-CTCAE v4 Grade 1 or less at the time of registration except for alopecia. Please note blood transfusion is allowed at baseline to bring HGB within study requirements, see section 5.2

3.1.13 Women of childbearing potential must have a negative serum pregnancy test performed within 7 days prior to the start of study drug. Post-menopausal women (defined as no menses for at least 1 year) and surgically sterilized women are not required to undergo a pregnancy test.

3.1.14 Subjects (men and women) of childbearing potential must agree to use adequate contraception beginning at the signing of the ICF until at least 30 days after the last dose of study drug. The definition of adequate contraception will be based on the judgment of the treating physician.

[figure not shown]
3.1.15 Willing and able to comply with the protocol, including follow-up visits and examinations

3.2 Conditions for Patient Ineligibility

- 3.2.1 Received systemic therapy with radionuclides (e.g., strontium-89, samarium-153, rhenium-186, or rhenium-188, or Radium Ra 223 dichloride) for the treatment of bony metastases
- 3.2.2 No prior invasive malignancy within the prior two years. However, patients with an early stage malignancy that is not expected to require treatment in the next 2 years (such as early stage, resected breast cancer or asymptomatic prostate cancer) are eligible
- 3.2.3 Untreated brain metastases.
- 3.2.4 Any other serious illness or medical condition that in the investigator's opinion would interfere with protocol treatment, such as but not limited to: Any active infection \geq National Cancer Institute Common Terminology Criteria for Adverse Events (NCI-CTCAE) version 4 Grade 2 or Cardiac failure New York Heart Association (NYHA) III or IV
- 3.2.5 Women who are pregnant or breast-feeding.
- 3.2.6 Inability to comply with the protocol and/or not willing or who will not be available for follow-up assessments.
- 3.2.7 Any condition which, in the investigator's opinion, makes the subject unsuitable for trial participation.
- 3.2.8 Concurrent anti-cancer therapy (chemotherapy, radiation therapy, surgery, immunotherapy, biologic therapy, or tumor embolization) other than Ra 223 dichloride.
- 3.2.9 Major surgery within 28 days of starting study drug. Central venous catheter placement is not considered major surgery.

4.0 TREATMENT

Schema:

Xofigo, 50 kBq/kg body weight (55kBq/kg body weight after NIST implementation), will be administered in the nuclear medicine department as a bolus intravenous (IV) injection (up to 1 minute) at intervals of every 4 weeks for up to 6 cycles. (Treatment should be administered

within +/- 3 days of cycle due date). Treatment delays of up to 14 days due to patient, physician or facility scheduling issues should be reported but will not constitute a deviation. Weight used for drug order is to be from pre-cycle assessment (done within 7 days prior to cycle start).

Patients are to be dosed based on drug order weight and weight collected the day of dosing, prior to dosing, is to only be used to confirm patient's weight has not changed by more than 10% (see section 5.1). Patient's dose is not to be adjusted based on day of weight.

For dosing please refer to appendices F and G

Filling of the syringe should take place in a safety bench or similar in the radiopharmacy/Nuclear Medicine department. Personnel should wear medical gloves and eye protection during syringe filling to prevent contamination of the radioactive solution to skin and eyes. The individual responsible for study drug preparation will draw the correct volume of study drug into a syringe.

The syringe should be handed over to the nuclear medicine personnel who will perform the injection. There is no need for shielding from alpha particle radiation during preparation and administration of the patient doses. (Alpha particles from radioactive decay of radium-223 and progeny are easily stopped by the thickness of a sheet of a paper or the walls of a glass vial.)

Aseptic technique should be used in the administration of Xofigo. The agent is administered as a slow bolus intravenous injection. After administration, the equipment used in connection with the preparation and administration of drug, are to be treated as radioactive waste and should be disposed in accordance with hospital procedure for the handling of radioactive material.

In general, the administration of radioactive drugs involves a potential risk for third parties, due to radiation from the patient and due to possible contamination by spilling urine or feces. When Xofigo has been injected intravenously into a patient, the risk for external radiation exposure to third parties is extremely low, due to the short range of the alpha particles (<100 μ m) and the very low portion of beta and gamma radiation. For these reasons the product can be administered on an outpatient basis.

Patients are informed to practice good hygiene for at least 1 week after study administration including washing hands, flushing the toilet several times after each use and washing clothes that are soiled with stool or urine promptly and separately from other clothes.

4.1 Duration of Treatment

Xofigo will be administered every 4 weeks for a maximum of 6 treatments. See 5.2 for reasons for study discontinuation. (Treatment should be administered within +/- 3 days). Treatment delays of up to 14 days due to patient, physician or facility scheduling issues should be reported but will not constitute a deviation.

5.0 TOXICITIES, DOSE MODIFICATIONS, AND MANAGEMENT

5.1

If labs are re-drawn post enrollment and prior to cycle 1 day 1 dosing, the following criteria are required to be met before dosing cycle 1:

- ANC must be ≥ 1.5 prior to day 1 dose of treatment (cycle 1)
- (PLT) count must be $\geq 100,000/\text{mm}^3$ prior to day 1 dose of treatment (cycle 1)
- Hemoglobin (Hgb) must be $\geq 9\text{g/dl}$ prior to day 1 dose of treatment (cycle 1)

A new course (cycle 2-6) of treatment should not begin until the following criteria are met:

- Platelets $\geq 50,000 \times 10^9/\text{L}$
- Granulocytes $\geq 1000 \times 10^9/\text{L}$ ($1000/\text{mm}^3$)
- Recovery from other treatment related, non-hematologic toxicities to \leq Grade 2
- Diarrhea \leq grade 2
- Nausea or vomiting \leq grade 2 or to baseline levels

If the patient does not meet these criteria delay day 1 until these requirements are met. Patients who require a treatment delay of more than 4 weeks from the scheduled treatment day due to toxicity will be removed from protocol treatment.

Weight prior to cycles 2-6 can be taken up to 7 days prior to dosing each cycle. Weight within 7 days of each cycle to be used for drug order and drug dosing for that cycle. Weight must again be assessed the day of drug administration, but this weight is only to be used to confirm patient's weight has not changed by $> 10\%$ since the prior assessment pre-dosing (for example 7 days prior). If weight has not changed by $> 10\%$ then, the patient is considered okay to treat. See section 6 subscript K for more details

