Myelosuppression; notably thrombocytopenia, neutropenia, pancytopenia, and leukopenia; has been reported in patients treated with Radium Ra 223 dichloride. In the randomized trial, complete blood counts (CBCs) were obtained every 4 weeks prior to each dose and the nadir CBCs and times of recovery were not well characterized. In a separate single-dose phase 1 study of Radium Ra 223 dichloride, neutrophil and platelet count nadirs occurred 2 to 3 weeks after Radium Ra 223 dichloride administration at doses that were up to 1 to 5 times the recommended dose, and most patients recovered approximately 6 to 8 weeks after administration

Hematologic evaluation of patients must be performed at baseline and prior to every dose of Radium Ra 223 dichloride. Before the first administration of Radium Ra 223 dichloride, the absolute neutrophil count (ANC) should be $\geq 1.5 \times 10^9/L$, the platelet count $\geq 100 \times 10^9/L$ and hemoglobin $\geq 9 \text{ g/dL}$. Before subsequent administrations of Radium Ra 223 dichloride, the ANC should be $\geq 1 \times 10^9/L$ and the platelet count $\geq 50 \times 10^9/L$. Patients with evidence of compromised bone marrow reserve should be monitored closely and provided with supportive care measures when clinically indicated. Discontinue Radium Ra 223 dichloride in patients who experience life-threatening complications despite supportive care for bone marrow failure.

The safety and efficacy of concomitant chemotherapy with Radium Ra 223 dichloride have not been established. Outside of a clinical trial, concomitant use with chemotherapy is not recommended due to the potential for additive myelosuppression. If chemotherapy, other systemic radioisotopes or hemibody external radiotherapy are administered during the treatment period, Radium Ra 223 dichloride should be discontinued.

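### The cycle 2–6 re-treatment thresholds in Protocol 5.1 carry the wrong unit and are printed 1,000 times higher than those in 9.1.11

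*Protocol*

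**What the plan says.** Section 5.1 of the Protocol has two sets of count criteria.

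- **Cycle 1, if labs are redrawn after enrolment.** The neutrophil line reads "ANC must be ≥ 1.5 prior to day 1 dose of treatment (cycle 1", with no unit. The platelet line reads "PLT) count must be $\geq 100,000/\text{mm}^3$ prior to day 1 dose of treatment (cycle 1".
- **Cycles 2 to 6.** The lines read "Platelets $\geq 50,000 \times 10^9/\text{L" and "Granulocytes $\geq 1000 \times 10^9/\text{L}$ ($1000/\text{mm}^3". The instruction that follows is: "If the patient does not meet these criteria delay day 1 until these requirements are met". A delay of more than 4 weeks because of toxicity takes the patient off protocol treatment.

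Section 9.1.11, under Bone Marrow Suppression, covers the same two decisions. Before the first administration, "the absolute neutrophil count (ANC) should be $\geq 1.5 \times 10^9/L$, the platelet count $\geq 100 \times 10^9/L". Before later administrations, "the ANC should be $\geq 1 \times 10^9/L$ and the platelet count $\geq 50 \times 10^9/L".

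Section 3.1.8 gives the entry minimums as "Absolute Neutrophil Count (ANC) \geq 1,500/mm³; Platelet (PLT) count \geq 100,000/mm³".

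**The concern.** The two sections that govern re-treatment do not give the same numbers. Nor can the granulocyte line in 5.1 be right in both of its forms, because 1000/mm³ and 1000 × 10^9/L are different quantities.

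Section 5.1 is where the delay instruction sits, so it is the working rule for up to five of a patient's six doses. Section 14.2 requires the study to be conducted as described in the approved protocol. If the printed × 10^9/L values are the rule, no patient qualifies for cycle 2 and every later dose given is a departure from the written criterion. If they are not the rule, sites must reconstruct a myelosuppression safety threshold from another section. The platelet line is the more exposed of the two, since it has no bracket beside it to show the intended value.

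**Working it through.** **Conversion.** 1 L = 10^6 mm³, so a count of x × 10^9/L equals x × 10^9 / 10^6 = 1,000x per mm³.

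**Check that the document uses the unit correctly elsewhere.** The first-dose platelet minimum is 100,000/mm³ in 3.1.8 and 5.1, and 100 × 10^9/L in 9.1.11. Since 100 × 1,000 = 100,000, these agree. The first-dose ANC minimum is 1,500/mm³ in 3.1.8 and 1.5 × 10^9/L in 9.1.11. Since 1.5 × 1,000 = 1,500, these agree too.

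**Cycle 2–6 criteria, converted to counts per mm³**

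| | 5.1 as printed | 9.1.11 | Ratio |
|---|---|---|---|
| Platelets | 50,000 × 1,000 = 50,000,000 | 50 × 1,000 = 50,000 | 1,000 |
| Granulocytes / ANC | 1,000 × 1,000 = 1,000,000 | 1 × 1,000 = 1,000 | 1,000 |

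**The granulocyte line against its own bracket.** The bracket, 1000/mm³, is 1000 / 1,000 = 1 × 10^9/L. The figure printed before it is 1000 × 10^9/L, again a factor of 1,000. The bracket agrees with 9.1.11 and the leading figure does not.

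**Against the first-dose minimums.** In 9.1.11, re-treatment requires lower counts than the first dose:

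- Platelets: 50,000 / 100,000 = 0.5
- ANC: 1,000 / 1,500 = 0.67

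With the 5.1 figures as printed, the order reverses:

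- Platelets: 50,000,000 / 100,000 = 500
- Granulocytes: 1,000,000 / 1,500 = 666.7

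**Which value is intended.** If the unit on both 5.1 lines is replaced by per mm³, they become 50,000/mm³ and 1,000/mm³. These are the 9.1.11 values exactly, and the second is also the bracket. One wrong unit label used on both lines explains the whole discrepancy.

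**Could it be a text-extraction fault?** This is unlikely. The same unit string appears on both lines, the bracket is intact, and 9.1.11 reads correctly.

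Section 5.1 says granulocytes where 9.1.11 says ANC. That difference in terms does not affect the factor of 1,000.

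**The case against.** The best case against giving this much weight is that the error exposes itself. No clinician could apply a minimum of 50 million platelets or 1 million granulocytes per mm³. The granulocyte line prints the correct value in its bracket, 9.1.11 states the correct rule for the same decision, and the cycle 1 criteria stand a few lines above. A dangerous unit error is one that gives a plausible wrong number, and this one does not. The claim that every patient would be delayed supposes a site that ignores all of these cues, and nothing in the documents suggests that any site would. On this view it is a minor editorial slip, and the mixed unit formats in 5.1 are a matter of style.

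Most of that stands as a statement about risk. The intended meaning can be recovered, the error is in the restrictive direction, and the 500 and 667 ratios add no consequence beyond the factor of 1,000. The missing unit on the cycle 1 ANC line is settled by 3.1.8 and 9.1.11 and carries no weight here.

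It does not remove the point. The wrong figures are in the dosing criterion itself, next to a mandatory delay instruction, and not in background text. An obvious intended meaning makes harm unlikely, but the printed threshold is still wrong.

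**Conclusion.** The concern holds. In the cycle 2–6 criteria of 5.1, both × 10^9/L figures are exactly 1,000 times those in 9.1.11, and the granulocyte line disagrees with its own bracket by the same factor. This is a unit-label error and not a competing clinical threshold.

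It should be fixed, but the practical risk is low. The intended values are recoverable, and the error does not permit dosing at low counts. Nothing in the documents shows that a patient was dosed or delayed wrongly because of it. Sample size, power, alpha and the analysis are not affected.

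The conversion needs no assumption. The statement that a literal reading would stop every patient at cycle 2 assumes that no patient reaches 500 times the first-dose platelet minimum or 667 times the first-dose neutrophil minimum.

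**What to change.** Amend the cycle 2–6 criteria in 5.1 to match 9.1.11:

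- Platelets ≥ 50 × 10^9/L (50,000/mm³)
- Granulocytes/ANC ≥ 1 × 10^9/L (1,000/mm³)

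In the same edit, give the cycle 1 ANC line its unit, 1.5 × 10^9/L (1,500/mm³), as in 3.1.8 and 9.1.11. Footnote C to the study calendar in section 6.0 repeats the ANC value of 1.5 without a unit and should be corrected at the same time.

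The cost is two corrected lines and the added unit in the next protocol amendment. Procedures, data collection and sample size do not change.
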